Randomized controlled trial comparing adult to pediatric colonoscope in obese patients.

NCT 06776913

Randomized controlled trial comparing adult to pediatric colonoscope in obese patients.

Corresponding author:

[name]

Email: [contact]

Address: [name]

Principal Investigator:

[name]

Email: [contact]

Address: [name]

Background

A colonoscopy is a routine procedure performed daily for various purposes, including colon cancer screening. Over time, colonoscopes have evolved and now come in different sizes, diameters, and flexibility levels. The choice of colonoscope typically depends on the endoscopist's preference, and anecdotal experience, with all types of instruments considered standard practice.

Several patient characteristics can make routine colonoscopy more challenging, such as diverticulosis and a history of previous surgeries, especially in the pelvic area. These challenging cases might influence the provider to choose one instrument over another, although there is a general lack of evidence demonstrating the superiority of specific colonoscopes in certain situations.

Obesity is one of the challenges encountered during routine colonoscopy. A retrospective study showed no difference in the performance of adult and pediatric scopes when matching the population's BMI. However, providers tend to choose adult scopes for higher BMI patients in unmatched populations. We designed this study to evaluate if adult and pediatric colonoscopes perform differently in obese patients, which both are considered standard practice in the study population.

Study objective.

The objective of this equivalence trial is to evaluate whether pediatric and adult colonoscopes achieve similar success rates in obese patients undergoing colonoscopy. Patients will be randomly assigned in a 1:1 ratio. The primary endpoint is the success rate of colonoscopy completion without switching instruments (defined in the main protocol).

Study hypothesis.

There is no significant difference between adult and pediatric colonoscopes in the evaluation of obese patients.

Study design.

Prospective randomized single-blinded Equivalence trial

- ➔ The patient is blinded regarding the instruments used.
- ➔ The endoscopist is not blinded. blinding is not feasible as the endoscopist would recognize the different instrument dimensions before the procedure.

Primary outcome

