- An investigator or research coordinator will contact the invited candidates by phone one week before the scheduled procedure. The study's purpose, intervention, and consent process will be discussed during this call, which will be documented in the patient's chart.
- Patients interested in participating will receive the consent form through DocuSign, with instructions on how to complete it online.
- A follow-up phone call will be made 1-2 days later to answer any questions the patient may have.

Rationale for Electronic Consent (E-Consent)

- Many procedures are scheduled through open access, meaning the patient is scheduled by a provider other than the one performing the procedure, often from a different department. In these cases, the patient may not meet the performing physician until the day of the procedure.
- E-consent allows patients more time to consider participation without the pressure of deciding on the day of the procedure.

Sample size calculations

Assuming a 93% success rate in both arms and no true difference between colonoscope types, we aim to test statistical equivalence using a two-sided type I error of 0.05 and power of 80%. A 10% margin (± 0.10) in success rate is considered clinically acceptable and forms the basis for the equivalence hypothesis:

$$H_0: |p_1 - p_2| \geq 0.1$$

$$H_1: |p_1 - p_2| < 0.1$$

Based on these assumptions, a fixed sample size of 112 participants per group (total N = 224) is required. To preserve operating characteristics under the group sequential framework, the maximum sample size is inflated by an estimated factor of 1.082, yielding a maximum of 122 participants per group (total N = 244). The interim analysis will occur after enrollment of 122 participants (61 per group). (Group Sequential Methods with Applications to Clinical Trials by Jennison and Turnbull (pages 149–150) [2].

Study Variables

Date of birth, gender, race, BMI, previous pelvic\abdominal surgery, diverticulosis, colon prep (adequate- inadequate), type of colonoscopy, insertion time, cecum and terminal ileum intubation success, and procedure time. Please refer to the data collection sheet for details of the variables above.

Data Analysis

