All statistical analyses will be conducted by a statistician from the Cleveland Clinic's Quantitative Health Sciences (CCF QHS) team, following the intention-to-treat (ITT) principle. This means that all randomized patients who receive one of the study interventions will be included in the primary analysis.

Baseline characteristics will be assessed for balance using standardized mean differences (SMDs), with a value less than 0.10 (absolute) indicating acceptable balance.

Missing data in baseline variables are expected to be minimal. If more than 5% of data are missing for any key variable, multiple imputation methods will be employed.

The primary outcome—successful completion of the colonoscopy (Yes/No)—will be analyzed as a binary endpoint. The effect of colonoscope type (adult vs. pediatric) will be evaluated using the Two One-Sided Tests (TOST) procedure, with a pre-specified equivalence margin of $\pm 10\%$. The absolute risk difference of 10% will also be translated into corresponding thresholds for odds ratios (OR = 2.72 or OR = 0.36) and relative risks (RR = 1.12 or RR = 0.893). Both unadjusted and adjusted logistic regression models, incorporating pre-specified covariates, will be used to estimate treatment

effects. Results will be presented as risk differences, relative risks, and odds ratios, with 95% confidence intervals derived via the g-computation method. Equivalence will be declared if the full confidence interval lies entirely within the specified equivalence range on each metric.

A per-protocol analysis will be conducted as a sensitivity analysis if there is substantial non-compliance. Additional sensitivity analyses will be considered to address missing data in outcome variables.

Secondary outcomes including cecal intubation rate (CIR), terminal ileum intubation rate (TIIR), insertion time (IT), use of ancillary maneuvers, withdrawal time, are considered independent of the primary outcome. Categorical secondary outcomes will be compared using chi-squared or Fisher's exact tests, while continuous variables will be analyzed using two-sample t-tests or Wilcoxon rank-sum tests as appropriate. Regression models adjusting for pre-specified covariates will also be considered.

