Repeatedly measured outcomes will be analyzed using mixed-effects models, with study group and time point included as fixed effects, and subject ID as a random effect to account for within-subject correlation. This approach is robust to data that are missing at random (MAR) or missing completely at random (MCAR).

Data Security

Data, including patient information and consent, will be stored electronically in the Redcap system\DocuSign which is password-protected and on the secure Cleveland Clinic network. If physical paper sheets were used, the physical paper sheets' information would be transferred to Redcap and shredded on the day of data gathering.

Interim analysis

A group sequential design with a single interim analysis at 50% enrollment is proposed. This design allows early trial termination for either efficacy (equivalence) or futility (non-equivalence), while preserving the overall type I error ($\alpha = 0.05$) and power ($1 - \beta = 0.80$).

The design employs Hwang-Shih-DeCani gamma error spending functions [1]:

- Type I error: $\gamma = -4$ (O'Brien-Fleming-like)
- Type II error: $\gamma = 1$ (Pocock-like)

Analysis Stage	Type I Error Spending (Cumulative)	Type II Error Spending (Cumulative)
Interim (50%)	0.00596	0.124
Final (100%)	0.05	0.2

A non-binding futility boundary is used. Z-stopping-boundaries are shown below.

Analysis Stage	Equivalence		Non-equivalence	
	upper	lower	upper	lower
Interim (50%)	2.749966	-2.749966	1.152821	-1.152821
Final (100%)	1.959964	-1.959964	1.959964	-1.959964

Possible Harm to Subjects

Both study arms are considered standard treatment, and no anticipated harm is related to the study.

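### The inflation factor 1.082 does not follow from the stated spending functions: at 0.05 per side they need about 1.18, and 122 per group gives about 77.5% power, not 80%, if futility is obeyed

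*Combined protocol and SAP*

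**What the plan says.** All references are to the combined protocol and SAP.

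- **Sample size calculations.** The planning case is "Assuming a 93% success rate in both arms and no true difference between colonoscope types", "using a two-sided type I error of 0.05 and power of 80" per cent. On the margin: "A 10% margin (± 0.10) in success rate is considered clinically acceptable". From this, "a fixed sample size of 112 participants per group (total N = 224) is required". Then "the maximum sample size is inflated by an estimated factor of 1.082, yielding a maximum of 122 participants per group (total N = 244"). The stated purpose is to preserve operating characteristics. No derivation of the factor is shown beyond a textbook page reference.
- **Study objective.** "Patients will be randomly assigned in a 1:1 ratio".
- **Data Analysis.** The scope effect is "evaluated using the Two One-Sided Tests (TOST) procedure", with equivalence declared from 95% confidence intervals.
- **Interim analysis.** One look at 50%. Type I spending has gamma = -4; for type II the entry is "Type II error: $\gamma = 1$ (Pocock-like"). Cumulative interim spends are 0.00596 and 0.124. Futility is non-binding. The printed equivalence boundaries are 2.749966 (interim) and 1.959964 (final). The section claims overall alpha 0.05 and power 0.80.

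**The concern.** The maximum sample size must pay for the power lost at the interim look. With gamma = 1, 62% of the type II error (0.1245 of 0.20) is spent there. Because futility is non-binding, the efficacy boundaries cannot be relaxed to recover any of it. An 8% increase looks small for that design. If the factor is too low, the 80% power stated in two sections is not what the stated design delivers, and a failure to show equivalence would be read against the wrong power.

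**Working it through.** **Inputs.** p = 0.93 in both arms, margin 0.10, 1:1 allocation, power 0.80 (Sample size calculations, Study objective); TOST (Data Analysis); information fraction t = 0.5, gammas -4 and 1, non-binding futility (Interim analysis). Assumption: normal approximation with unpooled variance.

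**1. Fixed sample size.** n = 2p(1-p)(z(1-a) + z(1-β/2))² / margin² = 13.02 × (z(1-a) + 1.282)².
- a = 0.05 per one-sided test: 13.02 × 2.926² = 111.5, so 112. This is the plan's figure.
- a = 0.025 per one-sided test: 13.02 × 3.242² = 136.8, so 137.

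The 112 therefore rests on 0.05 per side. Also, 112 × 1.082 = 121.2, so 122.

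**2. Spending at the interim.** f(t) = e(1 - exp(-γt)) / (1 - exp(-γ)), where e is the total error.
- Type I: e = 0.05, γ = -4 gives 0.00596, as printed.
- Type II: e = 0.20, γ = 1 gives 0.1245, as printed up to rounding.

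**3. Boundaries.**
- Efficacy, ignoring futility because it is non-binding: 2.514 then 1.664 at 0.05 per side; 2.750 then 1.981 at 0.025 per side. The printed 2.749966 therefore belongs to 0.025 per side.
- Interim futility: with no true difference, the total chance of stopping should be 0.1245 over both tails, so stop if |Z| > z(1 - 0.1245/2) = 1.536. The printed 1.152821 is z(1 - 0.1245), which puts the whole 0.1245 in each tail. That is a separate problem, and I do not use the value here.

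**4. Power at 122 per group.** The final standard error is √(0.1302/122) = 0.0327, so margin/SE is 3.061 at the end and 3.061 × √0.5 = 2.165 at the interim. Since 2.165 is below 2.514 and 2.750, this model gives no chance of early equivalence. (An exact binomial calculation with observed variances gives 7.0% at 0.05 per side and 3.6% at 0.025.) Power is then P(|Z1| ≤ 1.536 and |Z2| < 3.061 - c), with correlation √0.5 and c the final critical value.

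| Alpha per one-sided test | Final limit on abs(Z2) | Power, futility obeyed | Power, futility never acted on |
|---|---|---|---|
| 0.05 | 3.061 - 1.664 = 1.397 | 77.5% | 83.8% |
| 0.025 | 3.061 - 1.981 = 1.080 | 67.7% | 72.0% |

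With the printed 2.749966/1.959964, the second row becomes 68.5% and 72.9%. A 400,000-run binomial simulation with futility obeyed gives 76.4% and 67.4% for the two rows.

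**5. Factor needed for 80%.** Solve for the final margin/SE, then square its ratio to the fixed-design value.
- 0.05 per side: (3.182/2.926)² = 1.182; n = 131.8, so 132 per group.
- 0.025 per side: (3.499/3.242)² = 1.165; n = 159.4, so 160 per group.
- No futility rule, 0.05 per side: 1.013.

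So almost all of the required inflation comes from the type II spending. A factor near 1.08 appears with type II gamma = -1: the interim spend is 0.0755, futility is at |Z| > 1.777, the factor is 1.080 (121 per group), and power at 122 per group is 80.5%. At 0.025 per side the same change gives only 69.9%.

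**6. Price of gamma = -1.** At a true 10-point difference, the chance of a futility stop is Φ(2.165 - 1.536) = 74% with gamma = 1 and Φ(2.165 - 1.777) = 65% with gamma = -1.

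**The case against.** **The futility rule is non-binding.** If it is never acted on, 122 per group gives 83.8% at 0.05 per side. A reader might infer that 122 per group cannot reach 80% in any case; the plan's figures do not support that. But type II spending is normally powered on the footing that the boundary is followed, and the plan presents futility stopping as part of the design that keeps power at 0.80. This qualifies the point and does not remove it.

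**A binding boundary would nearly rescue 122.** With the final critical value relaxed to about 1.56, power at 0.05 per side is 79.6% and the need is about 124 per group. That contradicts the plan's non-binding wording and its final boundary of 1.959964, and the factor is then about 1.11, still not 1.082.

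**The shortfall is small.** At 0.05 per side it is 2.5 points, or about 10 patients per group, under an assumed 93% and a normal approximation. This stands.

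**The 68% belongs mostly elsewhere.** A reader might infer that the factor costs 12 points. It does not. At 0.025 per side, power is 72.0% even without futility, so 8.0 of the 12.3 missing points come from sizing 112 at 0.05 per side, and 4.3 from the futility look.

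**The factor has a cited source.** The plan calls it estimated and cites textbook pages that I cannot see. I can say that it does not reproduce from the stated design, not that no derivation exists.

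**Conclusion.** The point holds, with a modest size of its own. The factor 1.082 does not reproduce from the stated gammas, look and non-binding futility; at 0.05 per side, the level behind the 112, it is about 1.18. The stated 80% should read about 77.5% at 122 per group, given 93% in both arms, futility at |Z| > 1.536 and that rule obeyed. The larger gap, to about 68%, arises only if the printed boundaries and the 95% interval rule govern; it is then mainly a conflict between the alpha used for sizing and the alpha used for testing. The documents do not settle which per-side alpha is meant, so neither power figure can be taken as the trial's actual power until they do.

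**What to change.** 1. State the alpha per one-sided test, and make the boundaries and confidence interval level match it.
2. Recompute the futility boundary, inflation factor and power together, and replace the estimated factor with the computed one.
3. If 0.05 per side is confirmed, choose one of these:
   - Change the type II gamma to -1: factor 1.080, 80.5% power at 122 per group (80.0% by simulation). The cost is a lower chance of stopping early when the scopes truly differ by 10 points, about 65% instead of 74%.
   - Keep gamma = 1 and restate power as about 77.5%.
4. If 0.025 per side is kept, changing gamma is not enough (about 70%). Restate power as about 68% at 122 per group.

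None of these adds patients. The work is a revised design table and wording, to be finished before the interim look because the futility rule can end the trial there. Holding 80% with gamma = 1 and futility obeyed would instead take about 132 per group (20 more in total) at 0.05 per side, or about 160 per group (76 more in total) at 0.025 per side.

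### The lower odds-ratio equivalence limit of 0.36 does not match the 10-point margin (93% versus 83% gives 0.3675, or 1/2.72); the effect is small but the threshold should be corrected

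*Combined protocol and SAP*

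**What the plan says.** The sample size section sets the planning rate: "Assuming a 93% success rate in both arms and no true difference between colonoscope types". It sets the margin on the risk-difference scale: "A 10% margin (± 0.10) in success rate is considered clinically acceptable". The hypotheses there use the absolute difference, so they treat the two scopes symmetrically.

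The Data Analysis section carries that margin over to "corresponding thresholds for odds ratios (OR = 2.72 or OR = 0.36) and relative risks (RR = 1.12 or RR = 0.893". These limits are part of the decision rule: "Equivalence will be declared if the full confidence interval lies entirely within the specified equivalence range on each metric". The intervals are to be 95% intervals from g-computation, with unadjusted and adjusted logistic models. The comparison is described as adult versus pediatric, but the arm in the denominator of the ratios is not named. The plan gives no reason for an odds-ratio range whose two limits are not reciprocals.

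**The concern.** A range that expresses a symmetric margin as an odds ratio should have limits that are reciprocals of each other, as the relative-risk limits here are. If they are not, two things follow. One side of the range no longer represents the 10-point margin; here the lower side is slightly too wide, which is the permissive direction. And a confidence limit that falls between the printed and the correct value passes with one scope as reference and fails with the other. Because the odds-ratio range is one of the conditions for declaring equivalence, the question is whether this could alter the trial's conclusion.

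**Working it through.** **Inputs.** Success rate 93% in both arms, margin ±0.10, 112 per group for the fixed design and a maximum of 122 per group (Sample size calculations). The limits, the 95% interval and the decision rule come from Data Analysis. Since 93% plus 10 points exceeds 100%, the pair that defines the margin is 93% versus 83%.

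**1. Reproduce the printed limits.**
- Odds at 93%: 0.93/0.07 = 13.286. Odds at 83%: 0.83/0.17 = 4.882.
- Upper OR: 13.286/4.882 = 2.721. Printed 2.72; reproduced.
- Upper RR: 0.93/0.83 = 1.1205. Printed 1.12; reproduced.
- Lower RR: 1/1.12 = 0.8929. Printed 0.893; reproduced as the reciprocal (directly, 0.83/0.93 = 0.8925).
- Lower OR: 4.882/13.286 = 0.3675, and 1/2.72 = 0.3676. Printed 0.36; **not reproduced**.

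Rounding 0.3675 gives 0.37; only truncation gives 0.36. A base rate of about 93.25% would give 0.36, but its upper limit would then be 2.78, not 2.72.

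**2. What 0.36 means.**
- From 93%: odds 0.36 × 13.286 = 4.783, so p = 4.783/5.783 = 0.827. The deficit is 93.0 − 82.7 = 10.3 points.
- 1/0.36 = 2.78, against 2.72. On the log scale, ln(0.36) = −1.022 and ln(2.72) = 1.001.

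**3. Can the reference arm change the odds-ratio verdict?** Take 106/122 versus 109/122.
- OR = (106 × 13)/(109 × 16) = 0.790; ln OR = −0.2355.
- SE = √(1/106 + 1/16 + 1/109 + 1/13) = 0.3975.
- 95% CI: exp(−0.2355 ± 1.96 × 0.3975) = 0.3625 to 1.72. This is inside 0.36 to 2.72, so it passes.
- With the arms swapped, the upper limit is 1/0.3625 = 2.76. This is above 2.72, so it fails.
- The same table fails on the risk difference either way: −3/122 = −0.0246, SE = √[(106 × 16 + 109 × 13)/122³] = 0.0414, lower limit −0.0246 − 1.96 × 0.0414 = −0.106, beyond −0.10. The combined verdict is therefore unchanged.

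**4. How often?** All possible pairs of success counts were enumerated and weighted by their binomial probabilities. The intervals are unadjusted Wald (log scale for OR and RR) and replace the g-computation intervals. A flip is a verdict that changes when the arms are swapped.

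| Per arm, CI, true rates | Lower OR limit | OR-only flips | Combined flips |
|---|---|---|---|
| 122, 95%, 93%/93% | 0.36 | 0.05% | 0 |
| 122, 95%, 90%/90% | 0.36 | 1.6% | 0 |
| 122, 95%, 85%/85% | 0.36 | 3.1% | 0 |
| 112, 95%, 93%/93% | 0.36 | 1.3% | 1.3% |
| 122, 90%, 93%/93% | 0.36 | 4.6% | 4.6% |
| all of the above | 1/2.72 | 0 | 0 |
| 122, 95%, 93%/93% | 0.37 | 2.0% | 2.0% |

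At 122 per arm with 95% intervals, the combined rule passes equally often with 0.36 and with 1/2.72: 8.77% at 93%/93%, and 1.65% at 83% versus 93%, where the true difference lies at the margin. On the odds ratio alone, the pass rate at 83% versus 93% is 2.74% with 0.36 and 2.41% with 1/2.72.

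**5. Why 90% intervals are worth a row.** The fixed sample size reproduces with one-sided 0.05 per test: n = 2 × 0.93 × 0.07 × (1.645 + 1.282)²/0.10² = 111.5, so 112. That corresponds to a 90% interval, although the decision rule specifies 95%.

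**The case against.** The strongest reply is that this is a slip in the second decimal of a translated scale and decides nothing. The hypotheses and the TOST margin are on the risk difference, and equivalence needs the interval inside the range on every metric. At the planned maximum of 122 per arm with 95% intervals, 0.36 and 0.3676 give the same combined verdict. This stands, and it limits the point to a correction of a figure.

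A reader might infer that the trial's conclusion could turn on arm coding, or that the permissive limit makes a false declaration of equivalence more likely. The documents do not support either at the planned maximum size and interval level. The odds-ratio verdict never acts alone, and in the enumeration the tables that flip on it already fail another metric. The larger flip rates need a lower success rate with the odds ratio taken alone, 112 per arm, or 90% intervals.

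It would also be too strong to say that the plan leaves the direction of the ratio entirely open. Adult versus pediatric conventionally means adult over pediatric, although this is not spelled out.

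Finally, the correction does not touch a larger feature of the rule: at 122 per arm and 93%/93%, the 95% odds-ratio condition is met in about 9% of trials, against about 72% for the risk difference, with either lower limit. That is a separate matter.

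**Conclusion.** The printed 0.36 is wrong as a translation of the stated margin. The value is 0.3675 from 93% versus 83%, or 0.3676 as the reciprocal of the printed 2.72. The discrepancy is about 0.3 percentage points at 93%, in the permissive direction, and it makes the odds-ratio range slightly lopsided. Because the limit belongs to the pre-specified decision rule it should be corrected, but the priority is low: no effect on the combined verdict was found at 122 per arm with 95% intervals.

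This rests on reading the rule as requiring all three metrics, and on unadjusted Wald intervals; adjusted g-computation intervals could give slightly different results. That 0.36 arose by truncation is a likely explanation, not something the plan states.

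**What to change.** In Data Analysis, replace OR = 0.36 with OR = 1/2.72 (0.3676), and state that both odds-ratio limits derive from 93% versus 83%. Naming the reference arm in the same sentence would remove the remaining ambiguity about direction.

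Do not print the rounded 0.37 beside 2.72. Since 1/0.37 = 2.70, the range would then be lopsided the other way, and 2.0% of combined verdicts would flip at 122 per arm and 93%/93%, where the printed 0.36 causes none. With 1/2.72, no verdict depended on the reference arm in any setting tabulated.

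The cost is one figure and a short clause. The only downside is a marginally stricter lower odds-ratio limit.

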A composite of reaching the cecum, requiring less than 10 min for cecal intubation, without changing the scope type.

Secondary outcome

- ➔ cecal intubation rate (CIR)
- ➔ Terminal ileum intubation rate (TIIR): The provider will attempt terminal ileum in every patient for at least 2 minutes and up to 5 min.
- ➔ Insertion time (IT): time from insertion photo, to first cecal photo
- ➔ Ancillary maneuvers use (position change, pressure application, increase stiffness)
- ➔ Withdrawal time: time from terminal ileum picture or last cecal picture and rectal picture – 1 min per each intervention (polypectomy, cauterization...etc.)

Inclusion criteria

- BMI >30
- Screening and surveillance colonoscopy
- Male or female
- Age equal or more than 18 years

Exclusion criteria

- Colon surgery
- Therapeutic colonoscopy
- Inflammatory bowel disease
- Terminated procedure due to stool burden, stenosis, or obstructive mass.
- Colonoscopy for anemia
- History of incomplete colonoscopy due to technical difficulties

Randomization:

We will use the sealed envelope method for simple, stratified, randomization.

- Before the recruitment starts, we will prepare opaque sealed envelopes with a 1:1 ratio between the study groups, each envelope will have a serial number.
- On the day of the procedure, the endoscopist will be provided with a few envelopes (randomly selected serial numbers), he will choose one randomly and open it.
- All envelopes prepared before the recruitment process will be used during the study to ensure complete randomization and a 1:1 ratio between the study groups.
- The randomization will be stratified by providers performing the colonoscopy to ensure that each provider gets an equal assignment to both study groups to eliminate the bias that different providers' performances can introduce.

Study Operation:

1) Patient Invitation

- The research team will review the endoscopy schedule 1-2 weeks before the procedure date.

- All eligible candidates who meet the inclusion criteria will be invited to participate in the study.
- Candidates will be invited through A MyChart message or a mailed letter from the office of the provider performing the procedure.

2) Patient Consent

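### Randomisation is stratified by provider, but the analysis never names provider and does not say whether the unadjusted or the adjusted model decides equivalence

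*Combined protocol and SAP*

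**What the plan says.** The Randomization section of the combined protocol and SAP states: "The randomization will be stratified by providers performing the colonoscopy to ensure that each provider gets an equal assignment to both study groups". The reason given is "to eliminate the bias that different providers' performances can introduce". The Study objective section adds: "Patients will be randomly assigned in a 1:1 ratio".

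The Data Analysis section says that the effect of colonoscope type "will be evaluated using the Two One-Sided Tests (TOST) procedure". It then says: "Both unadjusted and adjusted logistic regression models, incorporating pre-specified covariates, will be used to estimate treatment" effects. Risk differences, relative risks and odds ratios are to be reported "with 95% confidence intervals derived via the g-computation method". The decision rule is: "Equivalence will be declared if the full confidence interval lies entirely within the specified equivalence range on each metric".

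The Study Variables section begins "Date of birth, gender, race, BMI, previous pelvic\abdominal surgery, diverticulosis, colon prep (adequate- inadequate), type of colonoscopy" and goes on to procedural times and intubation success. Provider is not in the list. The section refers to a data collection sheet that is not part of the document.

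The Interim analysis section gives Z boundaries for the interim and final looks but does not say which model produces Z.

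**The concern.** By stratifying on provider for the stated reason, the protocol treats provider performance as prognostic. The usual counterpart is an analysis that conditions on the stratification factor. Here the reader cannot tell whether provider enters the analysis at all.

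Two things are at stake. The more important one is that two models are planned and neither is primary, so one dataset can yield two equivalence verdicts. The choice also affects early stopping, because it determines the interim Z. The lesser one is precision: if provider is left out, the interval is slightly too wide, and any imbalance between arms within provider stays in the estimate.

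**Working it through.** **Inputs from the document.** Success rate 0.93 in both arms, margin 0.10, 112 per group fixed and 122 per group maximum (Sample size calculations); 95% intervals (Data Analysis). The number of providers and the spread of their success rates are not given, so every provider figure below is an assumption.

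**The plan's sample size.** n = 2p(1−p)(z(1−α) + z(1−β/2))² / margin² = 2 × 0.93 × 0.07 × (1.645 + 1.282)² / 0.10² = 111.5, so 112 per group. Then 112 × 1.082 = 121.2, so 122. The stated figures are reproduced with one-sided α = 0.05 and no provider term. With one-sided 0.025, which is what a 95% interval implies, the same formula gives 137. That mismatch is a separate matter, but it explains why the power figures in the table lie below 80%.

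**Expected failures.** 0.07 × 244 = 17.1 at the final analysis and 0.07 × 122 = 8.5 at the interim.

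**Cost of leaving provider out.** With exact balance within provider, the Mantel-Haenszel and unadjusted risk differences are the same number and only the standard error differs. Simulated probability of declaring equivalence at 122 per arm (true difference 0, 95% interval on the risk difference, no interim look, 20,000 trials per row; SD is between providers on the log-odds scale):

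| Providers | SD | Unadjusted | Stratified | Gain (points) |
|---|---|---|---|---|
| 5 | 0 | 71.8% | 71.9% | 0.1 |
| 5 | 0.5 | 72.3% | 72.9% | 0.6 |
| 5 | 1.0 | 72.8% | 75.4% | 2.6 |
| 5 | 1.5 | 73.3% | 78.5% | 5.2 |
| 10 | 0 | 72.1% | 72.3% | 0.2 |
| 10 | 0.5 | 72.6% | 73.4% | 0.8 |
| 10 | 1.0 | 72.7% | 75.7% | 3.0 |
| 10 | 1.5 | 74.0% | 80.2% | 6.2 |

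Mean standard errors at SD 1.0 are 0.0315 unadjusted against 0.0308 stratified with 5 providers (ratio 1.023), and 0.0320 against 0.0310 with 10 (ratio 1.032). A separate simulation with 8 providers and 15 patients per arm each took provider success rates from 83 to 99% or from 76 to 99.5%. The mean unadjusted standard error was 0.0326, against a true SD of 0.0321 or 0.0318 (ratios 1.016 and 1.025).

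**Type I error.** At a true difference of 0.10, the unadjusted test declares equivalence in 2.4 to 2.8% of trials, against a nominal 2.5%. The stratified test does so in 2.5 to 3.3%, so part of its gain at large SD comes from a slightly small standard error. With a 90% interval, the gain is between −0.8 and +1.2 points up to SD 1.0, and about 3 points at SD 1.5.

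**Two verdicts.** By logistic g-computation (risk difference, 95% interval, 1,500 trials per setting, a tiny ridge penalty to allow for separation), I compared the unadjusted model with one containing provider and one prognostic covariate. Share of trials with opposite verdicts:

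| Provider SD, covariate slope | 5 providers | 10 providers |
|---|---|---|
| 0, 0 | 2.3% | 3.2% |
| 0.5, 0.5 | 5.8% | 6.1% |
| 1.0, 0.5 | 7.8% | 8.8% |
| 1.0, 1.0 | 11.8% | 14.4% |

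**Sparse providers.** Assume equal volumes and a common 93% success rate. With 5 providers of 48.8 patients, 0.93^48.8 = 0.029, so the chance that at least one has no failures is 1 − (1 − 0.029)^5 = 14%. With 8 providers of 30.5 patients, 0.93^30.5 = 0.109 and the chance is 1 − (1 − 0.109)^8 = 60%. At the interim the corresponding chances are about 61% and 96%. A provider with no failures makes its fixed effect in a logistic model inestimable.

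**The case against.** The strongest reply is that the plan may already cover this. A reader might infer that the primary analysis does not use provider. The text does not support that: provider could be among the unlisted covariates, or on the data collection sheet. The Study Variables list is weak evidence of omission, since it also leaves out ancillary maneuvers, scope change and withdrawal time, which the trial needs for its outcomes. What can be said is that provider is never named.

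A reader might also infer that the stratification is wasted. It is not, because balance achieved by design protects against provider bias whether or not provider is modelled, and omitting it errs slightly on the conservative side.

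Nor can one say that the adjusted model as written will separate. It names no provider terms and the number of providers is unknown. Separation is a risk of one way of adding provider, and so bears on the choice of remedy.

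Finally, the decision rule does settle the choice among the three effect measures, since all must pass. All of this stands. It leaves untouched that neither model is designated primary, the covariates are unlisted and the source of Z is not stated.

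Exact balance within provider cannot be taken for granted either. No blocks within provider are described, the 1:1 guarantee depends on using every envelope, and the trial may stop at half enrolment.

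**Conclusion.** The point holds as a gap in specification with a small, free gain in precision attached. The main consequence is the undesignated model: opposite verdicts in about 2 to 14% of simulated trials, depending on assumed provider and covariate effects. The precision loss is minor: a standard error about 2 to 3% too large and about 0 to 3 points of power for a between-provider SD up to 1.0, rising to 5 to 6 points only at an assumed SD of 1.5. These power figures assume 5 or 10 providers, exact balance and a 95% interval; with a 90% interval the gain is smaller and can vanish. The effect of realised imbalance is not quantified. A reader might infer a false-positive problem from omitting the stratification factor, but the simulated rate of 2.4 to 2.8% shows no material inflation. No required sample size changes.

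**What to change.** Before the interim look, amend the Data Analysis and Interim analysis sections as follows.

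- Name one primary analysis that accounts for provider. A Mantel-Haenszel risk difference stratified by provider is a good candidate, because it tolerates providers with no failures and matches the ±0.10 hypothesis. Other approaches are defensible if chosen in advance.
- Fix the rule for pooling small-volume providers at the same time. Tie it to the interim look, since only patients are blinded and there is no unblinding date to refer to.
- State that this analysis supplies the interim and final Z and that its interval is the one compared with ±0.10.
- Reconcile this with the requirement that every metric must pass: either the risk difference alone decides, or the plan says how the relative risk and odds ratio intervals are obtained from the same primary analysis.
- List the pre-specified covariates, and keep the unadjusted and covariate-adjusted g-computation estimates as sensitivity analyses.
- Add provider ID to the Study Variables.

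The cost is SAP wording and one data field. Provider must already be known for each patient if randomisation is stratified on it. No extra patients are needed.
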